14.3.2 Analysis of secondary endpoint

- a) The expression levels of HIF1a, HIF2a, VEGF and their associated micro-RNAs 210, 155, and LET7b will be evaluated to check if any is altered at each of the dose levels administered.
- b) The following will be provided for the treatment combination:
 - Point estimate of median PFS time and 95% confidence interval by Kaplan-Meier along with survival plots.
 - Point estimate along with 95% confidence interval of the objective response rate (defined as SD+PR+CR, estimated).
 - Point estimate along with 95% confidence interval of the overall survival (OS).

14.4 SAMPLE SIZE AND POWER:

The number of patients to be enrolled in the Escalation Part 1 will depend upon the observed safety profile. The minimum number of patients required is 6 and the maximum is 12.

Of greatest interest for the expansion part 2 is to assess the progression free survival (PFS) for patients treated the dose of SLM in combination with a standard dose of axitinib in advance metastatic CCRCC. Historic median survival for patients within similar subgroup of advanced metastatic CCRCC is reported in the literature to be around 8 months. The goal of the pilot is to have a firsthand rough estimate of the median survival in our study population and define hypotheses for a subsequent larger trial.

Consequently, only a small sample would be required. To justify our sample, we will be operating under the assumption that the median survival will increase to 14 months in our treated population and that 90% upper confidence intervals will be constructed for the PFS (which would be equivalent to testing at 10% significance level, if statistical tests were to be carried). This may not be a stone-cut hypothesis; but reasonable for pilot justification. For the statistical analysis, exponential survival will be assumed and the associated survival rate estimated with maximum likelihood methods. A Wald statistic will be used to test this imperfect null hypothesis that median survival is equal to 8 months versus the one-sided alternative that it is greater than 14 months. With the planned enrollment of 19 patients accrued over 18 months and a total follow up for 14 months. The study will have 80% power to detect an increased survival of 6 months. The reason for this power justification is to put things into perspective and give an idea that one can actually glean some information out of this study—information that will serve as hypothesis generating for a larger trial. Estimates will be reported along with confidence intervals.

Pilot phase: Extra cohort with BSA based dose:

The primary objective of this pilot dose-finding study is to characterize the dose-concentration relationship and estimate the effective administered dose of selenium necessary to achieve the target blood concentration range informed by preclinical data. Preliminary data from the initial trial indicate a single fixed dose of selenium conferred significant variability in patient blood selenium concentrations at the end of the 14-day run-in. Patient body surface area (BSA) was found to be a contributing factor with patients of lower BSAs more frequently having higher blood selenium concentration, although none of which were within the targeted range of 35-45 μM . In light of these findings, a modified dosing scheme is being investigated which varies the dosage of selenium by BSA within a dose level to ensure less variability in the dose per m^2 administered.

Continual Reassessment Method

Dose escalation for this pilot study will be conducted using a continual reassessment method (CRM) in which the probability of exceeding a blood selenium concentration of 45 μM on Day 14 is being modeled. Prior probabilities of exceeding a blood selenium concentration of 45 μM on Day 14 were estimated based on preclinical and preliminary data from the initial trial. A one parameter logistic model with intercept set at 3 and an initial value of 1 for the slope will be used to estimate the dose-concentration relationship through sequential recursive Bayesian assessment. The target probability of exceeding 45 μM is $\leq 20\%$.

BSA	Dose Level ^a				
	1	2	3 ^b	4	5
1.50-1.79	2000	3000	4000	5000	6000
1.80-2.19	3000	4000	5000	6000	7000
2.20-2.49	4000	5000	6000	7000	8000
π_{45}^c	0.001	0.01	0.10	0.20	0.30

^aAll doses are mcg BID Day 1-14 then daily until progression.

^bStarting dose level.

^cProbability of exceeding 45 μM (prior)

[figure not shown]
Dosing will begin at dose level 3. Each cohort will enroll 2 evaluable patients. After each patient has completed the Day 14 evaluation, the following information will be provided to the statistical research team:

1. Blood selenium concentration on Day 14
2. DLTs, defined as any of the following treatment-related events occurring between Day 1 and 14 irrespective of outcome:
 - a. Clinically significant non-hematologic toxicity of Grade 3 or greater not related to underlying malignancy.
 - b. Severe hematological toxicity (Grade 4 neutropenia, Grade 3-4 febrile neutropenia, or Grade 4 thrombocytopenia).
 - c. Grade 4 nausea, vomiting, diarrhea, or electrolyte imbalances or Grade 3 nausea, vomiting, diarrhea and electrolyte imbalances lasting greater than 48 hours despite optimal medical intervention.

At which time, the dose-concentration model will be updated to obtain the recommended dose level for the subsequent cohort. Dose escalation will proceed one dose level at a time; skipping dose levels is not permitted.

Simulations

Simulations were conducted to evaluate the performance of the proposed design across various scenarios. More specifically, several potential underlying truths of the dose-concentration profiles were considered, and how the trial behaved in each of those scenarios was evaluated. Scenarios under consideration are those represented in the figure and table below. For each of the scenarios, simulations are based on the following specifications: cohorts of size 2 will enter the trial, a total of 10 patients will be used for each simulation, 1000 Monte Carlo replications are used, a one-parameter logistic model with starting parameter of 3 for the intercept and an initial slope of 1, no skipping dose levels, and starting at dose level 3.

	Dose Level				
	1	2	3	4	5
True Scenario 1	0.001	0.001	0.001	0.010	0.050
True Scenario 2	0.001	0.010	0.050	0.100	0.200
True Scenario 3 (Prior)	0.001	0.010	0.100	0.200	0.300
True Scenario 4	0.001	0.010	0.150	0.300	0.400
True Scenario 5	0.001	0.010	0.200	0.400	0.500

$\pi_{45} \leq 20\%$ are in green and $>20\%$ in red.

The operating characteristic using simulations for each scenario are summarized below.

		Dose Level				
		1	2	3	4	5
True Scenario 1:	% Selection	0.00	0.20	0.30	2.20	97.30
	% Subjects Treated	0.04	20.24	20.26	20.76	38.70
	# Subjects Treated	0.00	2.02	2.03	2.08	3.87
	Average Toxicities	0.00	0.00	0.01	0.02	0.21
	True Probabilities	0.001	0.001	0.001	0.010	0.050
True Scenario 2:	% Selection	0.00	2.70	6.50	22.50	68.30
	% Subjects Treated	0.52	23.80	24.92	22.98	27.78
	# Subjects Treated	0.05	2.38	2.49	2.30	2.78
	Average Toxicities	0.00	0.02	0.12	0.23	0.56
	True Probabilities	0.001	0.010	0.050	0.100	0.200
True Scenario 3:	% Selection	0.00	4.30	20.00	31.50	44.20
	% Subjects Treated	0.62	25.74	29.82	24.32	19.50
	# Subjects Treated	0.06	2.57	2.98	2.43	1.95
	Average Toxicities	0.00	0.02	0.30	0.48	0.59
	True Probabilities	0.001	0.010	0.100	0.200	0.300
True Scenario 4:	% Selection	0.00	7.20	33.70	36.30	22.80
	% Subjects Treated	0.74	28.50	34.00	22.76	14.00
	# Subjects Treated	0.07	2.85	3.40	2.28	1.40
	Average Toxicities	0.00	0.02	0.49	0.65	0.60
	True Probabilities	0.001	0.010	0.150	0.300	0.400
True Scenario 5:	% Selection	0.10	13.00	48.20	27.60	11.10
	% Subjects Treated	1.34	32.94	36.02	21.36	8.34
	# Subjects Treated	0.13	3.29	3.60	2.14	0.83
	Average Toxicities	0.00	0.03	0.70	0.86	0.41
	True Probabilities	0.001	0.010	0.200	0.400	0.500

$\pi_{45} \leq 20\%$ are in green and $>20\%$ in red.

Additional Safety Considerations

Preliminary data from the initial trial demonstrated the doses explored thus far were safe. In the Phase I dose-finding study of selenium in combination with irinotecan, all dose levels (max 7,200 mcg) evaluated were found to be safe but the upfront selenium run-in period was a week shorter than the current proposed dosing schedule (BID for 7 days vs BID for 14 days). As an additional safety precaution, patient accrual will pause if any DLTs are evidenced between Day 1 and 14 until the data and safety monitoring committee (DSMC) have reviewed the events and the appropriate course of action has been determined.

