1.0 OBJECTIVES

1.1 PRIMARY OBJECTIVES

1. To characterize the safety profile of combining SLM and axitinib in advanced metastatic CCRCC and;
2. To define the dose of SLM in combination with a standard dose of axitinib for Expansion Part 2 and future phase 2 trial (RP2D).
3. For the added pilot phase: The primary objective of this pilot dose-finding study is to characterize the dose-concentration relationship and estimate the effective administered dose of selenium necessary to achieve the target blood concentration range informed by preclinical data.

1.2 SECONDARY OBJECTIVES:

4. To determine that the dose of SLM administered is sufficient to alter the expression levels of HIF1a, HIF2a, VEGF and their associated micro-RNAs 210, 155, and LET7b.
5. To determine the SLM concentration when combined with axitinib.
6. To estimate the preliminary efficacy parameters of the combination of SLM and axitinib in terms of:
 1. Progression free survival (PFS),
 2. Objective response rate (SD+PR+CR), and
 3. Overall survival in patients with advanced metastatic CCRCC.

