2.3 CLINICAL STUDIES WITH SELENOMETHIONINE

Se compounds have been used in various clinical trials, mainly in chemo-prevention, at doses in the nutritional range (50 µg/day to 200 µg/day) without any toxicity (Casanovas). Since SLM was evaluated at higher doses 10 mg/kg/d in preclinical models where therapeutic synergy with anticancer drugs was demonstrated, clinical trials with escalating doses of SLM to achieve plasma concentration determined optimal in preclinical models were initiated at RPCI by [name], et al (Fakih) in combination with fixed dose of Irinotecan 125 mg/m² weekly. Different dose levels of SLM have been used (3200, 4000, 4800, 5600, and 7200 µg PO BID loading dose followed by once daily maintenance dose). A dose of 7200 µg/BID x 7 days followed by 7200 µg/QD for up to 36 days was determined sufficient and without toxicity. The only toxicity attributed to SLM was mild garlic-like odor (breath and urine) and was limited to G1 in about 50% of patients. This was seen more commonly during the induction SLM week and tended to ameliorate or disappear with prolonged treatment. No skin or nail toxicities secondary to SLM were documented.

Preliminary data from the initial trial indicate a single fixed dose of selenium conferred significant variability in patient blood selenium concentrations at the end of the 14-day run-in. Patient body surface area (BSA) was found to be a contributing factor with patients of lower BSAs more frequently having higher blood selenium concentration, although none of which were within the targeted range of 35-45 µM. Here we list the current subjects in 4 cohorts (C1: 4000 mcg, C2: 2500 mcg, C3: 3000 mcg and C4: 4000 mcg) and we list blood selenium concentration at D14, Cycle 2 and 7. There is clear difference in C 4 and C1 average blood concentration being higher in C 1 and associated with better responses.

Cohort	Pre	D14	C2	C7	Response
1	2.1	30.0	44.0	104.0	2CR, 1PR
2	2.0	14.0	21.0	25.0.	1PR, 1 PD
3	1.8	17.0.	25.0	43.0.	1PR, 2 PD
4	2.2	17.5	27	64	2 SD, 1 PD

CR (COMPLETE RESPONSE), PR (PARTIAL RESPONSE) SD (STABLE DISEASE) PD (PROGRESSIVE DISEASE)

IN LIGHT OF THESE FINDINGS, A MODIFIED DOSING SCHEME IS BEING INVESTIGATED WHICH VARIES THE DOSAGE OF SELENIUM BY BSA WITHIN A DOSE LEVEL TO ENSURE LESS VARIABILITY IN THE DOSE PER M2 ADMINISTERED.

2.4 HYPOXIA INDUCED FACTOR (HIF-A):

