After completing the Escalation Part 1 and based on the safety results, we will initiate an expanded cohort, Expansion Part 2 including a total of 19 patients with advanced metastatic CCRCC, to be treated with SLM 4000 in combination with axitinib 5 mg PO BID.

Up to 20 patients in the Expansion Part 2 and pilot phase will have mandatory biopsies at baseline before the start of SLM that will be repeated around day 14 (+/- 3 days) after starting SLM, at Cycle 3 (8 weeks +/- 3 days after first dose of SLM plus Axitinib) and preferably at disease progression, preferably from the same site of the previous biopsy, to study the expression of HIF-a and VEGF by immunohistochemistry (IHC), along with other biomarkers detailed in the correlative studies, before and after treatment with SLM. These tissues will be flash frozen and stored at -80 C to be processed later all at once for the proposed biomarkers.

The candidate patients for the biopsies will be chosen carefully by the treating oncologist and after discussion with the interventional/ body radiologist. Decision will be based on safety, ease of accessibility, tumor size and feasibility of getting the biopsy which can be done either on the primary renal tumor or metastatic site. Patient has to agree to get the biopsies, and sign consent form, after discussing the risks and benefits of the procedure with the provider.

All patients will have a peripheral blood draw at baseline before the start of SLM and repeated on day 14 after starting treatment. This blood will be stored and may be used later to study the protein expression of HIF1a, HIF2a, VEGF and level of SLM.

For Escalation Subjects: All patients will have a peripheral blood draw at baseline before the start of SLM and repeated on day 14 after starting treatment.

For Expansion Subjects: the peripheral blood draw will occur pre-dose and 2 hours post dosing on day 1 then 2 hours post dosing on Day 14 and at Cycles 2, 3, 4, 7, 10 and 13.

Pilot Phase: BSA based dosing. See additional details in protocol Section 14.4.

5.2

STUDY AGENT ADMINISTRATION

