12.3.1.1 Evaluation of Target Lesions

- Complete Response (CR): Disappearance of all target lesions. Any pathological lymph nodes (whether target or non-target) must have reduction in short axis to <10 mm.
- Partial Response (PR): At least a 30% decrease in the sum of the diameters of target lesions, taking as reference the baseline sum diameters.
- Progressive Disease (PD): At least a 20% increase in the sum of the diameters of target lesions, taking as reference the smallest sum on study (this includes the baseline sum if that is the smallest on study). In addition to the relative increase of 20%, the sum must also demonstrate an absolute increase of at least 5 mm. (Note: the appearance of one or more new lesions is also considered progression).
- Stable Disease (SD): Neither sufficient shrinkage to qualify for PR nor sufficient increase to qualify for PD, taking as reference the smallest sum diameters while on study.

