12.3.1.4 Duration of Response

- Duration of overall response: The duration of overall response is measured from the time measurement criteria are met for CR or PR (whichever is first recorded) until the first date that recurrent or progressive disease is objectively documented (taking as reference for progressive disease the smallest measurements recorded since the treatment started).
The duration of overall CR is measured from the time measurement criteria are first met for CR until the first date that progressive disease is objectively documented.
- Duration of stable disease: Stable disease is measured from the start of the treatment until the criteria for progression are met, taking as reference the smallest measurements recorded since the treatment started, including the baseline measurements.

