12.3.1.5 Progression-Free Survival

- PFS is defined as the duration of time from start of treatment to time of progression or death, whichever occurs first.

Table 4: For Patients with Measurable Disease (i.e., Target Disease)

Target Lesions	Non-Target Lesions	New Lesions	Overall Response	Best Overall Response when Confirmation is Required*
CR	CR	No	CR	≥ 4 wks. Confirmation**
CR	Non-CR/Non-PD	No	PR	≥ 4 wks. Confirmation**
CR	Not evaluated	No	PR	
PR	Non-CR/Non-PD/not evaluated	No	PR	
SD	Non-CR/Non-PD/not evaluated	No	SD	Documented at least once ≥ 4 wks. from baseline**
PD	Any	Yes or No	PD	no prior SD, PR or CR
Any	PD***	Yes or No	PD	
Any	Any	Yes	PD	

* See RECIST 1.1 manuscript for further details on what is evidence of a new lesion.
 ** Only for non-randomized trials with response as primary endpoint.
 *** In exceptional circumstances, unequivocal progression in non-target lesions may be accepted as disease progression.
Note: Patients with a global deterioration of health status requiring discontinuation of treatment without objective evidence of disease progression at that time should be reported as "*symptomatic deterioration*." Every effort should be made to document the objective progression even after discontinuation of treatment.

For Patients with Non-Measurable Disease (i.e., Non-Target Disease)

Non-Target Lesions	New Lesions	Overall Response
CR	No	CR
Non-CR/non-PD	No	Non-CR/non-PD*

Not all evaluated	No	not evaluated
Unequivocal PD	Yes or No	PD
Any	Yes	PD
* ‘Non-CR/non-PD’ is preferred over ‘stable disease’ for non-target disease since SD is increasingly used as an endpoint for assessment of efficacy in some trials so to assign this category when no lesions can be measured is not advised		

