14.6 ANALYSIS POPULATIONS

The safety population will consist of all subjects receiving at least 1 dose of study medication. All subjects who received at least one dose of study treatment and had at least 1 post-baseline response evaluation will be included in the efficacy analysis set. Following completion of the study, best response will be determined for each subject in accordance with RECIST v.1.1 guidelines and the objective response rate presented for each dose cohort.

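### The planned objective response rate counts stable disease, so it is a disease control rate under the wrong name, and no CR+PR rate is planned

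*Combined protocol and SAP*

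**What the plan says.** The rate is defined the same way in three places. Section 1.2 lists among the secondary efficacy parameters "Objective response rate (SD+PR+CR), and" overall survival. Section 14.2 repeats this. Section 14.3.2, the operative analysis section, asks for an estimate and 95% confidence interval of the "objective response rate (defined as SD+PR+CR, estimated". Section 14.6 has best response determined per subject under RECIST 1.1 and "the objective response rate presented for each dose cohort".

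Section 12 handles stable disease differently:

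- Section 12.3.1.1 defines SD as "Neither sufficient shrinkage to qualify for PR nor sufficient increase to qualify for PD".
- Section 12.3.1.4 says "The duration of overall response is measured from the time measurement criteria are met for CR or PR (whichever is first recorded"), and gives SD its own duration, counted from the start of treatment.
- Section 12.3.1.6 calls for confirmatory scans once an objective response has been documented.
- Table 4 has an entry for SD documented at least 4 weeks from baseline, but its footnote restricts that entry: "Only for non-randomized trials with response as primary endpoint". Response is a secondary endpoint here.

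The terms disease control rate and clinical benefit rate do not appear in the document.

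**The concern.** A patient whose tumour neither shrinks enough for PR nor grows enough for PD would count as an objective responder in Section 14, yet would have no duration of response under Section 12.3.1.4. Read literally with Section 12.3.1.6, every stable patient would also trigger confirmatory scans.

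The published rate and its interval would carry the name of a CR+PR rate. They could never be lower than one, and would be higher whenever any patient has SD as best response. Section 2.5 quotes a 44.2% objective response rate for axitinib. The document does not say which categories that figure counts, but a reader will set two figures with the same label side by side. Preliminary efficacy is an aim of the expansion part, and Section 14.4 says its results should generate hypotheses for a larger trial, so a mislabelled rate would be carried forward.

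The definition also blurs a contrast drawn in Section 2.3. Comparing cohorts 1 and 4, both at 4000 mcg, that section describes average selenium concentration as "higher in C 1 and associated with better responses".

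**Working it through.** The plan gives no target, threshold or power for the response rate, so there is no stated figure to reproduce. The check has two parts: the effect of the definition on the document's own data, and an illustration of how high the rate could be without any SLM effect.

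**1. The response table in Section 2.3**

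CR+PR rate = (CR + PR)/n. Planned rate = (CR + PR + SD)/n. Intervals are Clopper-Pearson 95%.

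| Group | CR | PR | SD | PD | n | CR+PR | SD+PR+CR |
|---|---|---|---|---|---|---|---|
| Cohort 1 (4000 mcg) | 2 | 1 | 0 | 0 | 3 | 3/3 | 3/3 |
| Cohort 2 (2500 mcg) | 0 | 1 | 0 | 1 | 2 | 1/2 | 1/2 |
| Cohort 3 (3000 mcg) | 0 | 1 | 0 | 2 | 3 | 1/3 | 1/3 |
| Cohort 4 (4000 mcg) | 0 | 0 | 2 | 1 | 3 | 0/3 | 2/3 |
| All | 2 | 3 | 2 | 4 | 11 | 5/11 = 45.5% (16.7–76.6%) | 7/11 = 63.6% (30.8–89.1%) |
| Cohorts 1+4 | 2 | 1 | 2 | 1 | 6 | 3/6 = 50% (11.8–88.2%) | 5/6 = 83.3% (35.9–99.6%) |

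- Overall difference: 2/11 = 18.2 percentage points.
- The 4000 mcg row matters because Section 5.1 describes the expansion patients as "to be treated with SLM 4000 in combination with axitinib 5 mg PO BID".
- Cohort 1 against cohort 4 is 3/3 against 0/3 by CR+PR, but 3/3 against 2/3 by the planned rate. Cohort 4 moves from last of the four cohorts to second.
- Cohort 2 lists two outcomes, although Section 5.1 planned three patients at 2500 mcg. If one is missing, n is 12 and the overall difference is 2/12 = 17 points, or 3/12 = 25 points if that patient had SD.

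**2. The 19-patient expansion**

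Each patient with SD as best response adds 1/19 = 5.3 points. Assuming, for illustration, 6 patients with CR or PR, the CR+PR rate is 31.6% (12.6–56.6%). With 2, 4, 6 or 8 SD patients the planned rate becomes 42.1%, 52.6%, 63.2% or 73.7% (48.8–90.9% for the last).

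**3. Illustration with no SLM effect**

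Assumptions: exponential PFS with median m months, and every patient progression-free at the first response scan counted as SD or better. Proportion = exp(−ln 2 × t/m), with t in months = weeks × 7/30.44, so 8, 10 and 18 weeks are 1.84, 2.30 and 4.14 months.

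| First response scan | m = 4.7 | m = 6.7 | m = 8 |
|---|---|---|---|
| 8 weeks | 76.2% | 82.7% | 85.3% |
| 10 weeks | 71.2% | 78.8% | 81.9% |
| 18 weeks | – | 65.2% | 69.9% |

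- The medians 6.7 and 4.7 months are the axitinib and sorafenib PFS values in Section 2.5; 4.7 is used only as a low bound. Section 14.4 gives 8 months as its null value, calling it median survival within a PFS justification; it is used here as a PFS median.
- Eight weeks is the interval in Section 12.2. Ten weeks adds the 14-day run-in. Eighteen weeks is the run-in plus four 28-day cycles (2 + 16), which applies only if response is first assigned at Cycle 5 Day 1, where Section 5.6 starts the CT disease assessments.

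**The case against.** The strongest reply is that the definition is printed openly each time the rate is defined, and is consistent across those three places. The endpoint is secondary and estimation-only, Section 14.4 makes PFS the main interest of the expansion, and no dose, sample size or go/no-go rule uses the rate. Section 12 never gives a formula for an objective response rate, so the conflict is inferred from its definitions. Section 14.1 promises counts and percentages for categorical variables, so CR, PR, SD and PD would normally be tabulated and CR+PR could be recovered.

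Most of this stands, and it limits the seriousness of the point. It does not remove it. Stating a composition does not make the label fit, the response section consistently separates SD from response, and no CR+PR rate with a confidence interval is planned anywhere.

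Other objections concern supporting material:

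- Section 12.3.1.3 makes best response depend on Table 4's confirmation criteria, which is in tension with reading the 4-week SD entry as not binding. The footnote still restricts that entry, so the text needs to be settled either way.
- The 18-week scenario is conditional. Sections 12.1 and 12.2.3 suggest that the Cycle 3 dual-energy CT can serve as an earlier response assessment.
- Section 2.3 does not say whether the listed outcomes are best or confirmed responses. It prints the categories themselves, so that table is not blurred; a report by cohort using the planned rate would be.

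**Conclusion.** The concern holds. Followed as written, the plan reports SD+PR+CR under the name objective response rate, out of line with its own Section 12, and gives no CR+PR estimate with an interval. On the document's own patients the effect is 64% against 45% overall and 83% against 50% at the expansion dose. These figures take the Section 2.3 outcomes as listed, and cohorts of two or three patients illustrate reporting only.

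Under the exponential assumption, a rate of about 79–85% at 8–10 weeks could arise with no SLM effect if median PFS is 6.7–8 months (71–76% for 4.7 months, and 65–70% for 6.7–8 months if response is first assigned at 18 weeks). A high value of the planned rate would therefore say little about added activity.

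This should be fixed before analysis, but it is not critical: the endpoint is secondary with no test attached, and PFS, OS, sample size and power are unaffected.

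**What to change.** In Sections 1.2, 14.2, 14.3.2 and 14.6, define the objective response rate as the proportion with a best overall response of CR or PR, with an exact 95% confidence interval. Report SD+PR+CR as a separate endpoint named disease control rate. For that rate, state a minimum SD duration and the scan at which SD can first be assigned, and reconcile Section 12.3.1.3 with the Table 4 footnote.

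The cost is protocol and SAP wording only. Best response is already determined per subject, so no new scans, patients or data are needed. The rate reported as objective response will be lower and still imprecise: for example, 8/19 = 42.1% has an exact 95% CI of 20.3–66.5%. The change makes the rate comparable with CR+PR rates. It does not make a small single arm precise, and it does not separate the contribution of SLM from that of axitinib.

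### The pilot aims at a concentration range of 35-45 µM, but its only specified model is a yes/no CRM for exceeding 45 µM; the 35 µM limit enters no analysis

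*Combined protocol and SAP*

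**What the plan says.** Section 1.1, item 3, and the pilot text in section 14.4 give the same objective. It has two parts: "The primary objective of this pilot dose-finding study is to characterize the dose-concentration relationship", and to "estimate the effective administered dose of selenium necessary to achieve the target blood concentration range informed by preclinical data". Sections 2.3 and 14.4 put the range at 35-45 µM. They explain that blood levels varied widely under fixed dosing, with lower-BSA patients more often higher, "although none of which were within the targeted range of 35-45" µM.

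Under Continual Reassessment Method, section 14.4 names one model: a one-parameter logistic CRM "in which the probability of exceeding a blood selenium concentration of 45" µM on Day 14 is modelled. It is this model that "will be used to estimate the dose-concentration relationship through sequential recursive Bayesian assessment". The criterion is one-sided: "The target probability of exceeding 45" µM is at most 20%. The prior values (0.001, 0.01, 0.10, 0.20 and 0.30 for levels 1-5) are also exceedance probabilities.

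The first item sent to the statistical team for each patient is "Blood selenium concentration on Day 14", so the measured value is available.

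Under Simulations, section 14.4 says "several potential underlying truths of the dose-concentration profiles were considered". Each of the five scenarios is a list of probabilities of exceeding 45 µM.

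Sections 14.2 and 14.3 contain neither the pilot objective nor a concentration analysis. Section 14.1 promises generic summaries (mean, SD, median, range) and data listings.

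**The concern.** The objective has a lower and an upper limit; the analysis has only the upper one. A yes/no outcome at 45 µM yields the probability of exceeding 45 µM by level. It does not yield a dose-concentration relationship, and it cannot divide the remaining patients into those in range and those below it.

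Falling short is what the earlier data showed. The Day-14 cohort averages in the section 2.3 table are 30.0, 14.0, 17.0 and 17.5 (read as µM), all below 35.

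The documents do not define what achieving the range means. The shares of patients below, within and above 35-45 µM are one natural reading, and the stated analysis estimates only the last of the three. If the definition is left open, it may be settled after the ten results are known.

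**Working it through.** **1. The plan's own simulation table.** I simulated a CRM using only the yes/no outcome above 45 µM: intercept 3, target 0.20, nearest level chosen, no skipping, five cohorts of two, 20,000 replications. The plan gives no prior for the slope; an exponential prior with mean 1 and a plug-in estimate fitted best. For Scenario 3, percent selected at levels 1-5:

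| | 1 | 2 | 3 | 4 | 5 |
|---|---|---|---|---|---|
| Plan | 0.0 | 4.3 | 20.0 | 31.5 | 44.2 |
| Start at level 3 (as stated) | 0.0 | 3.4 | 23.9 | 34.3 | 38.3 |
| Start at level 2 | 0.0 | 4.2 | 20.2 | 31.9 | 43.7 |

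As written, the table does not reproduce. With a level-2 start, selection agrees within 2.7 points across all five scenarios. The table is thus explained by the yes/no outcome at 45 µM, with no input from 35 µM. The starting-level discrepancy needs separate reconciliation and does not affect this point.

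**2. Spread, for illustration.** Log-SD of the Day-8 values by level 1-7 in section 9.1, Table 3: 0.26, 0.30, 0.16, 0.29, 0.14, 0.20, 0.36; pooled 0.27 on 23 degrees of freedom. Those were plasma troughs after one week of twice-daily fixed dosing. The pilot doses by BSA and samples 2 hours post-dose on Day 14, so its spread may differ. I use a log-SD *s* of 0.15-0.35.

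**3. What a given exceedance implies.** Let concentration be log-normal with P(>45) = p. Then the median is 45·exp(−z·s), where z is the upper-p normal quantile, and

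P(<35) = Φ(z − ln(45/35)/s), with ln(45/35) = 0.2513; P(35-45) = 1 − p − P(<35).

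Example: p = 0.20, s = 0.27 gives Φ(0.8416 − 0.9308) = Φ(−0.0892) = 46.4% below, and 100 − 20 − 46.4 = 33.6% in range.

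The largest in-range share any dose could give has its median at √(35 × 45) = 39.7 µM and equals 2Φ(0.2513/(2s)) − 1.

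| s | p = 20%: below / in range | p = 5%: below / in range | Maximum in range |
|---|---|---|---|
| 0.15 | 20.2% / 59.8% | 48.8% / 46.2% | 59.8% |
| 0.20 | 33.9% / 46.1% | 65.1% / 29.9% | 47.0% |
| 0.27 | 46.4% / 33.6% | 76.2% / 18.8% | 35.8% |
| 0.35 | 54.9% / 25.1% | 82.3% / 12.7% | 28.0% |

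The 5% column matches level 5 in Scenario 1, which the plan's simulations select 97.3% of the time. One exceedance value fits very different in-range shares, depending on s.

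**4. Dose per m² within a level** (table in section 14.4). Level 3: 4,000/1.79 = 2,235 to 5,000/1.80 = 2,778 mcg/m². Level 4: 6,000/2.19 = 2,740 to 5,000/1.50 = 3,333. Level 5: 7,000/2.19 = 3,196 to 6,000/1.50 = 4,000. Levels 4 and 5 overlap, so a per-level estimate must average over BSA.

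**5. What ten patients can deliver.** I simulated 20,000 pilots per value of s. Assumptions: 2/6/2 patients at levels 3/4/5, BSA uniform on 1.50-2.49, true median proportional to mcg/m², 20% exceedance at 3,000 mcg/m², and log concentration regressed on log mcg/m² with a free slope. At s = 0.27 the middle 95% of estimates are:

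| Quantity | True | Estimates |
|---|---|---|
| P(<35) at 2,500 mcg/m² | 72% | 25-99% |
| P(35-45) at 3,000 mcg/m² | 34% | 20-54% |
| P(>45) at 3,500 mcg/m² | 39% | 5-82% |

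The fitted slope is negative in about 9% of pilots (1% at s = 0.15, 14% at s = 0.35). Counts alone are less precise: 2 of 6 in range has an exact 95% interval of 4-78%.

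**The case against.** The strongest reply is that the one-sided criterion is a good proxy. In the table above, the in-range share at 20% exceedance is within 3 points of the best any dose could reach. Low values are not ignored either: they count as non-exceedances and move the CRM upward. The poor figures at 5% exceedance arise at the top level, where there is nothing higher to choose. All of this stands, and it is why the point concerns estimation and not the level selected.

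The earlier cohort averages came from fixed doses of 2,500-4,000 mcg, while the pilot starts at 4,000-6,000 mcg by BSA. They show where the problem has been, not where pilot patients will fall. That also stands.

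With ten patients, the counts could be read from a listing under section 14.1. But those summaries are not tied to the objective, use no 35 µM limit and give no interval or dose relationship. Reading counts off a listing is not a planned analysis.

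The target itself is unsettled: section 2.6.2 gives a desired level of about 30 µM and section 2.6.3 cites at least 30 µM. This is a further reason to reconcile the text before fixing the analysis.

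Finally, a regression on ten patients is imprecise, and real spread may be larger: the two 4,000 mcg cohorts in section 2.3 averaged 30.0 and 17.5 on Day 14, a ratio of 1.7. The results therefore need a descriptive label. Reducing ten measured values to yes/no loses still more.

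**Conclusion.** The concern holds. The stated analysis of the pilot's primary objective estimates exceedance of the upper limit and cannot estimate attainment of the range. This follows from the text alone and needs no distributional assumption.

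The size is illustrative: 20% exceedance is compatible with 20-55% of patients below 35 µM and 25-60% in range; 5% exceedance with 49-82% below and 13-46% in range. These figures assume log-normal concentrations and a log-SD of 0.15-0.35 taken from a different sampling time and schedule. Nothing here shows that the CRM selects a wrong level. The plan should be changed on this point, but the fault does not undermine the pilot's conduct.

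**What to change.** Add to section 14.4, as the pilot's primary concentration analysis:

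*Day-14 concentrations below, within and above 35-45 µM will be counted by dose level with exact 95% intervals. Log Day-14 (2-hour post-dose) concentration will be regressed on log administered mcg/m². Estimated P(<35), P(35-45) and P(>45 µM) with 95% intervals will be reported for each dose level used, averaged over the BSA of the patients treated at that level. Results are descriptive.*

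Earlier-phase Day-14 2-hour values may be added as a supportive fit with a cohort term, with the pilot-only fit shown beside it.

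The sponsor should also reconcile the range objective (sections 1.1 and 14.4) with the one-sided criterion in section 14.4, and state what achieving the range means. No dose or escalation rule is proposed.

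The cost is SAP wording and modest analysis work. Day-14 values already go to the statisticians, and a 2-hour Day-14 draw is in all three lab calendars (sections 20.0, 20.1 and 20.2). The price is a log-normal assumption and wide intervals.
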